5.4. Initial Assessment

In Aim 1, study patients will complete demographics and a 30-60 minutes interview in which they will watch an education video and complete the UR-GOAL tool and provide feedback. Patients in Aim 2 will complete baseline assessments with the study coordinator, watch an education video, and complete the UR-GOAL tool. Caregivers in Aim 2 will complete baseline assessments with the study coordinator and watch an education video.

6.0. UR-GOAL Intervention Tool

The proposed tool consists of three components: BWS to elicit patient preferences, fitness assessment, and prognostic awareness assessment (Figure 1). In addition, an education video will also be included. The education tool provides information on the diagnosis, epidemiology, symptoms, risk factors, and prognosis of AML, as well as goals of AML treatment and treatment approaches.

Figure 1: Components of the UR-GOAL communication tool

6.1.Best-worst scaling

BWS consists of 10 choice tasks, with 4 attributes per task. Patients will be presented with 4 attributes at a time, in which a patient is asked to rank the most and least important attribute when choosing a treatment (Figure 2). This process then repeats 10 times until all attributes are evaluated. Based on our qualitative study of older patients with AML and oncologists,⁴³ we selected eight attributes that are important in treatment decision making. At completion, a summary containing the ranking of the attributes will be provided to the patient and oncologist. The patient summary also includes a question prompt list (based on their top four attributes).

Figure 2: Best-Worst Scaling showing 4 options

Please consider how important the priorities below are to you when choosing a cancer treatment. Considering only these 4 priorities, what is the MOST IMPORTANT and which is the LEAST IMPORTANT?

Most Important

Least Important

	 Daily activities Whether or not I will be able to do the activities that I do now without help	
	 Quality of life How likely it is that my quality of life will change	
	 Location of treatment Whether a treatment requires a one-month stay at the hospital versus receiving it in the hospital and going home on the same day	
	 Survival How likely it is that I will be alive one year after treatment	

6.2. Fitness Assessment:

We will include assessments (e.g., physical function, nutritional status; Table 1) that evaluate fitness and are important in decision-making for both patient and oncologist.¹³ At completion, a summary containing the patient's fitness level will be provided to the oncologists.

Table 1: Questionnaires that will be included in the tool

Fitness domain	Assessments
Physical function	Activities of daily living, instrumental activities of daily living, number of falls, Short Physical Performance Battery
Nutritional status	Weight loss in the prior 6 months
Comorbidity	Hearing and eyesight
Psychological health	Geriatric Depression scale
Social support	Patient's social support Living situation
Medications	Number of medications
Cognition	Mini-Cog

6.3. Prognostic Awareness Assessment:

We will incorporate assessment of prognostic awareness (i.e., chance of cure and survival estimates, their information preference (i.e., do they prefer treatment success rate presented in percentages, words, fractions, or they wanted to hear about a previous patient that the physician treated), and whether conversation about prognosis would be helpful to them. At completion, a summary contacting this information will be provided to the oncologists.

As described above, the generated summaries are tailored and intended to improve communication between the patient and oncologist during the decision-making process.

6.4. Education Video

As the overall goal of the study is to improve patient-physician communication, we created an education video for patients. The video contains basic information about the diagnosis, epidemiology, symptoms, risk factors, and prognosis of AML, as well as goals of AML treatment and treatment approaches. We created this video because of two main reasons: 1) Our preliminary data suggest that many older patients may not understand the AML diagnosis and treatment approaches given the acuity, 2) The video provides an overview of AML which will help patients complete the tool subsequently (e.g., the tool will ask patients if they are willing to trade quality of life for higher remission, and the education video provides information on what remission means in the context of the different treatments). The video is not part of standard of care. We developed this video based on feedback from the leukemia and bone marrow transplant and geriatric oncology groups at WCI.

The video is available for view using this link:

<https://rochester.box.com/s/m25aidirevgzaeumgvnpymd3mck1lxhy>

7.0. Treatment Protocol

7.1. Study Outline

We will screen and consent eligible patients of treating physicians at WCI and WCI-affiliated centers.

[figure not shown]
For Aim 1, the study team will conduct an in-person or zoom/phone interview for 30-60 minutes. First, we will explain the rationale of the study. Second, patients will use the communication tool. Third, we will conduct an interview to elicit feedback about the communication tool. This feedback will be used to adapt the tool for Aim 2.

For Aim 2 and Exploratory Aim (Figure 3), the study subject will complete baseline measures and utilize the UR-GOAL communication tool either in-person or via zoom/phone. Following this, patients will complete the usability testing form. The patient (and caregiver if available) will have a visit with their primary oncologist and the clinical encounter will be audio-recorded. The study staff will provide an audio recorder to the physician for in-person or phone visits, and the zoom recording feature will be used for zoom visits. All parties present for recorded visits, including: enrolled patients, any accompanying caregivers, family or friends, the oncologist, and any other physicians or health care providers not participating in the study will be fully aware that the conversation is being audio-recorded before any recording begins, in addition to the prior written consent of enrolled patients. Patients, caregivers and oncology physicians may receive copies of these recordings at their request.

The post-intervention measures, including the qualitative interviews, for patients and caregivers will be completed within 1-2 weeks of the patient's encounter with the primary oncologist either in-person or via phone/zoom. The interviews will be conducted separately. Patients will participate in a semi-structured interview for 30-60 minutes during which feedback will be elicited. Enrolled caregivers will also participate in a separate semi-structured interview for 30-60 minutes during which feedback will be elicited. Oncologist will also complete the post-intervention assessments (surveys) within 1-2 weeks of the patients encounter. The semi-structured interviews with oncologists will be conducted at any time during the study, after at least one of their patients have completed the study procedures.

To assess priorities longitudinally, patients will complete the BWS on the tool at 1, 2, 3, and 6 months.

Figure 3: Study Procedures (Aim 2 and Exploratory Aim)

Video: <https://rochester.box.com/s/0zgtsct34770282re0na6eopzho6105d>

1

7.2. Assessments of the Participants

Demographic, clinical, and cancer characteristics will be collected.

7.2.1. Demographics – Patient, Caregiver, and Oncologist

Patient and caregiver's age, date of birth, race, ethnicity, gender, highest level of education achieved, employment status, and marital status. This will only be collected at baseline.

Oncologist's name, date of birth, race, five-digit zip code, ethnicity, and gender will be collected.

7.2.2. Clinical and Cancer Characteristics - Patient

ECOG performance status, diagnosis, prior hematologic malignancies, cytogenetic risk group and treatment regimen will be abstracted from the medical records. This information will only be collected at baseline.

7.2.3. Measures

Measures will be collected via the UR-GOAL tool, done in person, or mailed to the participants.

7.2.2.1. Physical Function and Functional Status (Baseline Only - Patient)

Short Physical Performance Battery (SPPB; baseline only): The SPPB is an objective physical assessment evaluating lower extremity physical function. It is comprised of a four-meter walk, repeated chair stands and a balance test. Impairment on SPPB testing has been shown to be predictive of short-term mortality and nursing home admission in community-dwelling older adults.⁴⁶ If in-person SPPB cannot be performed, we will

perform the virtual SPPB via the phone/zoom, which evaluates the participants' perceived ability to perform above tests (walking, repeated chair stands, and balance).⁴⁷

Activities of daily living (ADL): ADLs are measures of self-care. ADL independence will be assessed using the Katz Index of Independence in Activities of Daily Living, commonly referred to as the Katz ADL. The Katz ADL is the most appropriate instrument to assess functional status as a measurement of the client's ability to perform activities of daily living independently. Clinicians typically use the tool to detect problems in performing activities of daily living and to plan care accordingly. The Index ranks adequacy of performance in the six functions of *bathing, dressing, toileting, transferring, continence, and feeding*. Clients are scored yes/no for independence in each of the six functions. A score of 6 indicates full function, 4 indicates moderate impairment, and 2 or less indicates severe functional impairment.⁴⁸

Instrumental Activities of Daily Living (IADL): Self-reported functional status will be assessed using the IADL subscale of the Multidimensional Functional Assessment Questionnaire: Older American Resources and Services (OARS). The IADL subscale consists of seven questions rated on a three-point Likert scale. It measures the degree to which an activity can be performed independently.⁴⁹

Fall History: A self-reported history of falls in the past three months will be recorded. A history of a recent fall has been demonstrated to be independently predictive of increased risk for chemotherapy toxicity in older cancer patients.⁵⁰

7.2.2.2. Nutritional Status (Baseline Only - Patient)

Screenings for nutritional deficit will be performed with body mass index (BMI) evaluation and self-reported weight loss.

7.2.2.3. Comorbidity (Baseline Only - Patient and Caregiver)

OARS Comorbidity: Patients and caregivers report coexisting illnesses and indicate the degree to which these comorbidities interfere with their daily activities.⁵¹

Patients and caregivers also self-report their perceived levels of eyesight and hearing.

7.2.2.4. Psychological Health (Baseline and Post-Intervention – Patient and Caregiver)

General Anxiety Disorder-7: A 7-item screening tool for anxiety.⁵²

Geriatric Depression Scale-15: A 15-item valid and reliable screening tool for depression in older adults.⁵³ This will be used for patients.

Patient Health Questionnaire-2 (PHQ-2): A 2-item valid and reliable screening tool for depression in the general population.⁵⁴ This will be used for caregivers.

7.2.2.5. Social Support (Baseline Only - Patient)

OARS Medical Social Support: A 13-item questionnaire for patients regarding persons involved in medical social support as well as perception of overall support.^{51,55}

Patients also self-report their living situation and their main social support.

7.2.2.6. Medications (Baseline Only - Patient)

Medications: We will record all prescription and non-prescription medications, dosage and frequencies from the medical records. Polypharmacy is defined as the use of 5 or more medications.

7.2.2.7. Cognition (Baseline Only - Patient)

Mini-Cog (baseline only): A 3-item screening tool for cognitive impairment in older adults.⁵⁶

7.2.2.8. Communication Self-Efficacy (Baseline and Post-intervention – Patient and Caregiver)

Perceived Efficacy in Patient-Physician Interactions (PEPPI): A valid and reliable assessment of perceived self-efficacy of older patients interacting with physicians.⁵⁷

Perceived Efficacy in Caregiver-Physician Interactions (PECPI): A valid and reliable assessment of perceived self-efficacy of caregivers interacting with physicians.⁵⁸

7.2.2.9. Patient-Centered Communication (Post-Intervention Only – Patient and Caregiver)

Patient-Centered Communication in Cancer Care (PCC-Ca-36): A questionnaire assessing patient-centered communication in six domains: exchanging information, making decisions, fostering healing relationships, enabling patient self-management, managing uncertainty, and responding to emotions.⁵⁹ We will adapt the PCC-Ca-6 for caregivers.

7.2.2.10. Shared Decision-Making (Post-Intervention Only – Patient, Caregiver, and Physician)

Shared Decision-Making Questionnaire (SDM-Q-9): A 9-item reliable questionnaire assessing patient satisfaction with the medical decision-making process.⁶⁰

Shared Decision-Making Questionnaire (SDM-Q-Doc): A 9-item reliable questionnaire assessing physician satisfaction with the medical decision-making process.⁶¹

CollaboRATE Measure: A 3-item questionnaire assessing patient, caregiver, and

physician shared decision-making.⁶²

Preparation for Decision Making Scale: A 10-item questionnaire assessing patients' and caregivers' perception of how useful the communication tool is in preparing them to communicate with their physician at a consultation focused on making a health decision.⁶³

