4.1.4. Duration

Aim 1: The qualitative section of this study involves interviewing consented patients for 30-60 minutes. They will watch an education video and use the UR-GOAL tool and feedback can be provided during the interview. Study participants will be interviewed by the study team either in-person (in a private space) or via phone/zoom. Interviews will be audio-recorded, uploaded to Box, and subsequently deleted from the audio-recorder.

Aim 2 and Exploratory Aim: After completing baseline measures, watching an education video, and completing the UR-GOAL tool, study participants will participate in a semi-structured interview with the study team for 30-60 minutes either in-person or via phone/zoom. The post-intervention measures will be completed within 1-2 weeks of the patient's encounter with the primary oncologist either in-person or via phone/zoom. Caregivers will complete baseline measures and watch an education video. They will participate in a separate semi-structured interview with the study team for 30-60 minutes either in-person or via phone/zoom. The post-intervention measures will be completed within 1-2 weeks of the patient's encounter with the primary oncologist either in-person or via phone/zoom. After the study is completed, participant data will be maintained for 7 years at URMC and will be kept in a password-protected database.

Oncologist will also complete the post-intervention assessments (surveys) within 1-2 weeks of the patients encounter. Oncologists will participate in a semi-structured interview with the study team for 30-60 minutes either in-person or via phone/zoom., after at least one of their patients have completed the tool. The semi-structured interviews with oncologists will be conducted at any time during the study. After the study is completed, participant data will be maintained for 7 years at URMC and will be kept in a password-protected database.

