9.0. Data Management

9.1. Data Collection Table

9.1.1. Aim 1

	Eligibility and Consent Form	Assessment
Informed Consent	X	
Demographics		X
Clinical and Cancer Characteristics		X
Qualitative Interview		X
Short Physical Performance Battery/Virtual Short Physical Performance Battery, Activities of Daily Living, Instrumental Activities of Daily Living, Fall History		X
Nutritional Status		X
Comorbidity		X
Geriatric Depression Scale-15 (GDS-15), Generalized Anxiety Disorder-7 (GAD-7)		X
Social Support		X
Medications		X
Mini-Cog		X
Information and Decision-Making Preferences		X
Disease Understanding - Patient		X

9.1.2. Aim 2

a) Patients

	SCHEDULE OF DATA COLLECTION			
	Eligibility and Consent Form	Baseline Assessment (week 0)	Post-intervention Assessment (week 1-2)	Month 1, 2, 3, and 6
Informed Consent	X			
Demographics		X		
Clinical and Cancer Characteristics		X		
Qualitative Interview			X	
Short Physical Performance Battery/Virtual Short Physical Performance Battery, Activities of Daily Living, Instrumental Activities of Daily Living, Fall History		X		
Nutritional Status		X		
Comorbidity		X		
Geriatric Depression Scale-15 (GDS-15), Generalized Anxiety Disorder-7 (GAD-7)		X	X	
Social Support		X		
Medications		X		
Mini-Cog		X		
Perceived Efficacy in Patient-Physician Interactions (PEPPI)		X	X	
Patient-Centered Communication in Cancer Care (PCC-Ca-36)			X	
Shared Decision-Making (SDM-Q-9) ^a			X	
CollaboRATE Measure			X	
Preparation for Decision Making Scale			X	
Patient Disease Knowledge		X	X	
Information and Decision-Making Preferences - Patient		X		
Disease Understanding - Patient		X	X	
Decisional Conflict Scale			X	
Decisional Regret Scale and Was it Worth It Questionnaire				X
BWS component only of the tool				X
EQ-5D-5L			X	X
Usability (Usability questions)			X	

b) Caregivers

	SCHEDULE OF DATA COLLECTION		
	Eligibility and Consent Form	Baseline Assessment (week 0)	Post-intervention Assessment (week 1-2)
Informed Consent	X		
Demographics		X	
Qualitative Interview			X
Comorbidity		X	
Patient Health Questionnaire-2 (PHQ-2), Generalized Anxiety Disorder-7 (GAD-7)		X	X
Perceived Efficacy in Caregiver-Physician Interactions (PECPI)		X	X
Patient-Centered Communication in Cancer Care (PCC-Ca-6) – adapted caregiver version			X
Ryff's Environmental Mastery		X	X
CollaboRATE Measure			X
Preparation for Decision Making Scale			X
Caregiver Disease Knowledge		X	X
Information and Decision-Making Preferences – Caregiver		X	
Disease Understanding – Caregiver		X	X

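### Caregivers rate the communication tool's usefulness, but the plan gives them only the education video and records no contact with the tool, so their score is ambiguous

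*Combined protocol and SAP*

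**What the plan says.** Section 7.2.2.10 describes the Preparation for Decision Making Scale as a 10-item questionnaire, for both patients and caregivers, on their "perception of how useful the communication tool is in preparing them to communicate with their physician". Schedule 9.1.2(b), for caregivers, carries the row "Preparation for Decision Making Scale" at the week 1-2 post-intervention assessment.

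On what caregivers receive, section 4.1.4 states: "Caregivers will complete baseline measures and watch an education video". Section 5.4 agrees: "Caregivers in Aim 2 will complete baseline assessments with the study coordinator and watch an education video". The sentence just before that one sets out the patient's part: "Patients in Aim 2 will complete baseline assessments with the study coordinator, watch an education video, and complete the UR-GOAL tool".

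Section 6.0 defines the tool: "The proposed tool consists of three components: BWS to elicit patient preferences, fitness assessment, and prognostic awareness assessment". It then mentions the video as a further inclusion. For the best-worst scaling (BWS) component, section 6.1 says that "a summary containing the ranking of the attributes will be provided to the patient and oncologist". Sections 6.2 and 6.3 send the fitness and prognostic-awareness summaries to oncologists only.

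**The concern.** A usefulness rating can be read only if it is known what the rater used. Here the named object of the rating is the communication tool, while the caregiver's planned contact is with the video. A low caregiver score could mean that the tool prepared them poorly or that they never saw it. A high score could be praise for the video.

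The secondary aim (section 2.2) includes caregivers in the evaluation of the tool, and section 7.2.2.16 gives the usability questions to patients and oncologists only. This scale is therefore the one caregiver questionnaire described as rating the tool. Section 8.2.2 says the measures outside the feasibility and usability criteria are collected to prepare a larger trial. An ambiguous caregiver score would carry into that planning.

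**Working it through.** No arithmetic applies beyond a count. The check sets the measure beside the planned exposure, element by element.

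| Element | Patient | Caregiver | Oncologist | Source |
|---|---|---|---|---|
| Education video | yes | yes | not stated | 4.1.4, 5.4 |
| BWS component | completes | no | – | 5.4, 6.1 |
| Fitness assessment | completes | no | – | 5.4, 6.2 |
| Prognostic-awareness assessment | completes | no | – | 5.4, 6.3 |
| BWS summary | receives | not named | receives | 6.1 |
| Fitness summary | not named | not named | receives | 6.2 |
| Prognostic-awareness summary | not named | not named | receives | 6.3 |
| Usability questions | yes | no | yes | 7.2.2.16, 9.1.2 |
| Preparation for Decision Making Scale | yes | yes | no | 7.2.2.10, 9.1.2 |

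1. *Planned direct exposure.* Caregivers are assigned 0 of the 3 tool components and 0 of the 3 summaries. Their one planned item is the video.
2. *Is the video the tool?* Section 6.0 lists three components without it. Section 5.4 names video and tool as separate steps for patients. Section 6.4 says the video helps patients with the tool they complete afterwards. On these texts the two are distinct.
3. *Indirect exposure.* Section 7.1 has the caregiver, if available, join the visit with the oncologist, who will hold the summaries. The patient holds a copy of the BWS summary with a question prompt list, and nothing stops a caregiver from reading it. But section 8.1.3, on access to data collected through the tool, names only the research team and the treating physician or designee, and no form in 9.1.2(b) is described as asking whether the caregiver saw the tool.
4. *Result.* The caregiver scores can mix three kinds of rater: those who met the tool or its summary, those who rate the video, and those with no basis for rating the tool. No planned variable separates them.
5. *Size.* Section 3.7 plans 15 patients, with caregivers if available. Assuming one caregiver per patient, at most 15 caregivers are affected at target enrolment.

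**The case against.** The strongest reply is that the video belongs to the intervention. It is section 6.4 of a section titled as the UR-GOAL intervention tool, and section 6.0 includes it and calls it an education tool. On that broad reading, caregivers received part of the package and can sensibly say how well it prepared them. This stands as far as it goes: the term is used loosely. But 7.2.2.10 speaks of the communication tool, which 6.0 defines by its three components, and nothing says that the caregiver form refers to the video.

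Secondly, the questionnaire itself and Figures 1 and 3 are not in the text available for review. The caregiver form may already name the video. If so, the protocol need only say so.

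Thirdly, each enrolled caregiver has a separate interview of 30 to 60 minutes in the same 1-2 week window, where exposure could come up. That helps, but the protocol does not require the question, and an interview remark is not a recorded variable linked to the score.

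Fourthly, section 7.2.3 allows measures to be collected through the UR-GOAL tool. That is a mode of data capture and assigns no tool component to caregivers.

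The limits on importance are correct. The scale is not among the section 2.5 metrics (recruitment, System Usability Scale, interviews). It is outside the >50% completion rule, which concerns patients. Being post-intervention only, it cannot enter the paired baseline-to-post tests.

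**Conclusion.** The mismatch is in the text: caregivers are asked about the tool, are given the video, and have no recorded contact with the tool. The caregiver score is ambiguous without exposure data. The consequence is limited to reading these ratings, from at most about 15 caregivers, and to using them in planning the later trial.

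Three stronger readings are tempting, and the documents do not support them:

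- That caregivers rate something they certainly never received. Indirect contact is possible, and the video sits within section 6.0.
- That the score is worthless or undermines Aim 2. The caregiver contribution under section 2.5 is the interview, which has its own analysis method in 8.2.2, and no feasibility decision uses this scale.
- That patient and caregiver scores will be pooled. No such plan appears.

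The conclusion assumes that the caregiver form follows the description in 7.2.2.10 and that the missing figures assign caregivers nothing beyond sections 4.1.4 and 5.4.

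**What to change.** - In the caregiver version of the scale, name the education video as what is being rated, and say so in 7.2.2.10.
- Add one yes/no item at the caregiver post-intervention assessment in 9.1.2(b): did you see, or help complete, the tool or its summary?
- State in 8.2.2 that any tool-directed caregiver rating will be described only for those who answer yes, with their number given.

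The cost is a reworded stem, one extra item and one analysis sentence. Sample size and study procedures do not change. The drawback is that the exposed subgroup will be small and may be empty, in which case the study has no quantitative caregiver rating of the tool and should report that plainly. Giving caregivers the summary, dropping the scale for them, or defining the tool to include the video would also remove the mismatch. The last would still leave it unknown which part was rated.
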